Primary Statistical Hypothesis	This study is a single-arm, small sample clinical study without any hypothesis testing. It can be considered reasonable if up to 2 failed cases of primary safety endpoint event occur. It can be considered reasonable if up to 2 failed cases of endpoint event occur in each of the five primary effectiveness endpoints.
Statistical Test Method	Descriptive statistics will be conducted for the endpoint events.
Sample Size Parameters	This study is a single-arm, small sample clinical study without any hypothesis testing. Twenty subjects (10 with ICD and 10 with CRT-D) will be enrolled. It is assumed that the attrition should not be more than 2 cases in each group, so that at least 8 subjects shall be included in the final analysis for each group.

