#### **11.4. Enrollment Controls**

According to the study protocol, 10 ICD subjects (at least 2 single chamber ICDs and 2 dual chamber ICDs) and 10 CRT-D subjects will be enrolled. It should be ensured that at least 8 ICD subjects (at least 1 single chamber ICD and 1 dual chamber ICD) and 8 CRT-D subjects undergo protocol required MR scan and complete all the sequences. It should be ensured that both single coil and dual coil defibrillation leads are implanted. It should be ensured that both straight and spiral LV leads are implanted. Subject enrollment might be expanded to meet the above requirement to support product registration.

Generally, one individual center may not enroll more than 10 subjects. Investigational sites will be notified when the enrollment goal is close to being reached and once enrollment is complete.

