## **13. Statistical Considerations**

### **13.1. Primary Endpoints**

#### **13.1.1. Primary Safety Endpoint: MR Scan-Related ImageReady System Complication Free Rate**

The primary safety endpoint of the MR ICD study will be assessed for all subjects who undergo any portion of the study-required MR scan sequences. Safety will be confirmed by evaluating the MR scan related ImageReady System complication-free rate (CFR) between the MR Scan and the MRI Visit + 1 Month.

For the purpose of this endpoint, a MR scan-related ImageReady System complication will be defined as those complications that are related to the MR scan and ImageReady System. All complications that the site reports as related to the MR scan and ImageReady System will be adjudicated by an external committee for relation to the MR scan. Complications that are determined to be associated with the MR scan will be considered MR scan-related complications and count against this endpoint. Complication is defined as serious adverse event or permanent loss of device functions (i.e. pacing or defibrillation).

The performance goal of the primary safety endpoint for the ENABLE MRI study (MR scan related ImageReady System complication free rate) was 90%. There is no hypothesis testing in the MR ICD study, and it can be considered reasonable if up to 2 failed cases of primary safety endpoint event may occur. Descriptive statistics will be conducted for the endpoint events.

The data set for the primary safety endpoint will include all subjects who undergo the study-required MR scan sequences (scan sequences initiated, whether complete or not). The time window for MRI + 1 Month visit is 30±7 days post MR scan, so it will capture events within at least 23 days post scan. In this small sample size study, missing data will be excluded.

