### **13.3. Sample Size**

The MR ICD study is a small sample size study without any formal hypothesis testing. Twenty subjects (10 with ICD and 10 with CRT-D) will be enrolled. It is assumed that the attrition should not be more than 2 cases in each group, so that at least 8 ICD subjects (at least 1 single chamber and 1 dual chamber ICD) and 8 CRT-D subjects shall undergo required MR scan and complete all the sequences. Sample size might be expanded to meet this assumption.

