#### **13.4.3. Data Set, Subgroups and Missing Data**

The data set for the safety endpoint will include all subjects who undergo the study-required MR scan sequences (scan sequences initiated, whether complete or not). The data set for the effectiveness endpoint will only include subjects who undergo the study-required MR scan and complete all the sequences, and will not include subjects that meet any of the following exclusions:

- Has a medically necessary scan between implant and the MRI + 1 Month Visit
- Fails to meet labeled MRI Conditions of Use

- Experiences a lead-related complication between MRI Visit and the MRI + 1 Month Visit MRI

Subjects whose average RV sensed amplitude <5mV pre-MR scan will also be excluded for primary effectiveness endpoint 3 assessment, and subjects whose average LV sensed amplitude <5mV pre-MR scan will also be excluded for primary effectiveness endpoint 5 assessment.

There is no formal subgroup analysis in the MR ICD study, however, descriptions may be grouped on study site, subject sex, device type (single chamber ICD, dual chamber ICD and CRT-D), etc.

The primary endpoints for the MR ICD study are comparisons between MRI Visit and the MRI + 1 Month Visit, absence of either comparator will be missing data for that endpoint. Missing data will be excluded for endpoint assessment in this small sample size MR ICD study.

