### 5.1.1 Primary efficacy endpoint analysis:

The primary effectiveness endpoints are defined as ‘a success based on the specified criteria conditions earlier’, otherwise it’s a failure (event) .

All the 5- primary endpoints are based on Implant population,

- Pre-MR Scan vs. 1 Month Post-MR Scan RV shocking impedance
- Pre-MR Scan vs. 1 Month Post-MR Scan RV Pacing Threshold at 0.5 ms
- Pre-MR scan vs. 1 Month Post-MR Scan RV Sensed Amplitude
- Pre-MR Scan- vs. 1 Month Post-MR Scan LV Pacing Threshold at 0.5 ms
- Pre-MR scan vs. 1 Month Post-MR Scan LV Sensed Amplitude

are summarized descriptively with counts and percentages presenting 95% Clopper-Pearson confidence interval with two-sided exact binomial confidence bound at 95% will be presented to anticipate that the endpoint success is more than the lower bound of the confidence limits.

The time window for MRI + 1 Month visit is  $30\pm 7$  days post MR scan, so it will capture events within at least 23 days post scan for all the endpoints and Missing data will not be considered in the denominator part while deriving confidence limits and performance goals.

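### Effectiveness endpoints: subjects scanned but without a 1-month value are dropped while the benchmark stays at two failures, so losing one failing subject can turn a missed benchmark into a met one

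*Combined protocol and SAP*

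**What the plan says.** **Missing data.** Protocol 13.4.3 describes the primary endpoints as comparisons of the MRI Visit with the MRI + 1 Month Visit and adds that "absence of either comparator will be missing data for that endpoint"; missing data are then left out of endpoint assessment. Section 13.1.1 (safety) states "In this small sample size study, missing data will be excluded", and the same sentence closes each of 13.1.2 to 13.1.6 (effectiveness 1 to 5). The SAP follows: missing data are excluded for safety (3.1), and for effectiveness "Missing data will not be considered in the denominator part" (5.1.1). SAP 7.3 rules out imputation.

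**Benchmark.** The synopsis says "This study is a single-arm, small sample clinical study without any hypothesis testing". It and 13.1.1 to 13.1.6 call the result reasonable with up to two failed cases per endpoint. The limit is not scaled to the number evaluable. SAP 3.2 repeats the idea for effectiveness but omits the number, so the limit there comes from the protocol.

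**Numbers.** Section 13.3: "Twenty subjects (10 with ICD and 10 with CRT-D) will be enrolled" and "It is assumed that the attrition should not be more than 2 cases in each group". The synopsis concludes that "at least 8 subjects shall be included in the final analysis for each group". The enrolment control in 11.4 is worded differently: besides a matching floor for ICD subjects, it requires that at least "8 CRT-D subjects undergo protocol required MR scan and complete all the sequences". Section 13.3 uses the same scan-completion condition, and enrolment may be expanded to meet it.

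**A separate exclusion.** Sections 13.1.2 to 13.1.6 and 13.4.3, and SAP 3.2 and 4.1, also remove from the effectiveness set any subject with a lead-related complication between the MRI Visit and the 1-month visit.

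**The concern.** A fixed failure count judged on whoever remains is sensitive to who drops out. A subject who would have failed at 1 month but has no value leaves the numerator as well as the denominator, and the limit does not tighten in response.

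The reasons for a missing value need not be neutral. System revision or removal, or death, can both prevent the measurement and reflect the failure that the endpoint is meant to detect. With about 20 subjects for the RV endpoints, about 10 for the LV endpoints and a limit of two, one such loss can change the conclusion. That conclusion forms part of the Phase I data intended to support registration in China (protocol section 9).

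The floor of eight per group does not guard against this. As written in 11.4 and 13.3, it is satisfied once the scan sequences are complete, so a loss between the scan and the 1-month visit triggers no expansion.

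**Working it through.** **Inputs**
- Enrolled: 20, as 10 ICD and 10 CRT-D (13.3). RV endpoints can apply to all 20, LV endpoints to the 10 CRT-D subjects.
- Attrition: at most 2 per group (13.3).
- Benchmark: at most 2 failures per endpoint (synopsis; 13.1.2 to 13.1.6).
- Performance goals of the reference study: 87% for pacing threshold (13.1.3, 13.1.5) and 85% for sensed amplitude (13.1.4, 13.1.6). Their complements, 13% and 15%, serve below as illustrative failure rates. No goal is quoted for shocking impedance.
- Intervals: two-sided 95% Clopper-Pearson (SAP 5.1.1).

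**1. The plan's own figure.** 10 − 2 = 8 per group and 16 in total. This reproduces.

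**2. One failing subject lost after the scan**

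| | Successes | Failures | Success rate (95% CI) | Benchmark |
|---|---|---|---|---|
| RV, complete | 17/20 | 3 | 85.0% (62.1 to 96.8) | not met |
| RV, one failing subject lost | 17/19 | 2 | 89.5% (66.9 to 98.7) | met |
| LV, complete | 7/10 | 3 | 70.0% (34.8 to 93.3) | not met |
| LV, one failing subject lost | 7/9 | 2 | 77.8% (40.0 to 97.2) | met |

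**3. Success rate implied by exactly two failures,** (n − 2)/n: 90% at n = 20, 87.5% at 16, 80% at 10 and 75% at 8. The limit loosens as subjects are lost.

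**4. Upper bound.** Assume that all allowed attrition is after the scan, that two failures are observed and that every lost subject failed.
- RV: 2/16 = 12.5% observed; (2 + 4)/20 = 30%.
- LV: 2/8 = 25% observed; (2 + 2)/10 = 40%.

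Subjects lost before the scan do not enter this calculation.

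**5. Chance of meeting the benchmark,** P(X ≤ 2) with X ~ Bin(n, p).

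Loss unrelated to outcome:

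| Failure rate p | n = 20 | n = 16 | n = 10 | n = 8 |
|---|---|---|---|---|
| 13% | 0.508 | 0.654 | 0.869 | 0.926 |
| 15% | 0.405 | 0.561 | 0.820 | 0.895 |

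Loss related to outcome: suppose each failing subject is lost with probability q. The documents give no value for q, so a range is shown. Observed failures are then Bin(N, p(1 − q)). At p = 15%:

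| N | q = 0 | q = 0.2 | q = 0.5 |
|---|---|---|---|
| 20 | 0.405 | 0.563 | 0.814 |
| 10 | 0.820 | 0.891 | 0.966 |

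At N = 20 and q = 0.5 the expected number of failing subjects lost is 20 × 0.15 × 0.5 = 1.5, below the four losses that the plan allows.

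**6. What counting missing as failure would do.** With m missing, the observed failures allowed are 2 − m: one if m = 1, none if m = 2. With m ≥ 3 the limit cannot be met. At four missing of 20, an RV endpoint would miss it with no observed failure at all. This is why the count is useful as a display and unsuitable as the rule.

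**The case against.** **Safety.** A reader might infer that a scan-related death before the 1-month visit would drop out of the primary safety endpoint. The documents do not support that. The safety endpoint counts events, and its set is everyone whose scan sequences were started (13.1.1). Complications found to be associated with the scan count against it. Serious adverse events and deaths must be reported within 24 hours, the Clinical Events Committee must review deaths (21.4, 21.7), and data collected up to withdrawal may be used (11.2). A reported complication is therefore an observed event. What remains is a gap in wording: 13.1.1 and SAP 3.1 exclude missing data for safety, and 13.4.3 refers to the primary endpoints without exempting safety.

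**Direction.** It is tempting to say that every exclusion moves the count toward the limit. It does not. Dropping a would-be success leaves the failure count unchanged; only the loss of a failing subject lowers it.

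**Size.** The 30% and 40% figures could be read as forecasts. Enrolment starts at consent (11.1), so attrition includes subjects never implanted or never scanned, who cannot fail a comparison across the scan. Enrolment may also be expanded. The figures are bounds only.

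**Mechanism.** Subjects with a lead-related complication leave through their own exclusion, not through the missing-data rule. For a subject who attends but cannot be captured, 13.1.3 and 13.1.5 treat anything other than a rise within the limit as an event, which might be read as covering that case. Section 13.4.3 treats an absent value as missing, and the plan does not say which prevails.

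**Transparency.** No test is planned, and the SAP provides exact intervals, follow-up compliance at 1 month, a death listing, per-subject lead listings and missed visits as deviations (5.1.1, 5.3.1, 5.3.3, 7.3). A careful reader could rebuild much of the picture. This lowers the stakes, but the interval is not tied to the limit of two and no table puts the number missing beside the failure count.

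**Conclusion.** The point holds for the five effectiveness endpoints. Excluding scanned subjects who lack a 1-month value, together with a fixed limit of two failures, means that one outcome-related loss after the scan can reverse the reading: 3/20 becomes 2/19, or 3/10 becomes 2/9. The expansion rule does not respond to such losses, and no planned display shows the dependence.

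The reversal is arithmetic and rests only on the lost subject being one who would have failed. The bounds of 6/20 and 4/10 need all allowed attrition to be post-scan and failing. The probabilities rest on illustrative failure rates and, for outcome-related loss, on an assumed q. The benchmark is descriptive, so meeting it is an informal conclusion, though it is the only one that the plan states.

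For safety the finding is limited to wording that should be made explicit. The change is worth making and is inexpensive.

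**What to change.** 1. **Safety wording (protocol 13.1.1 and 13.4.3; SAP 3.1).** State that any adjudicated scan-related complication between the scan and the end of the 1-month window counts, whether or not the 1-month visit took place.
2. **Effectiveness tables (protocol 13.1.2 to 13.1.6 and 13.4.3; SAP 5.1.1).** For each endpoint, among scanned subjects who otherwise qualify, report the number missing and the failure count in two forms, as observed and with missing counted as failure, each beside the limit of two. Label the second a sensitivity display and say that it is not a new decision rule.
3. **Missing for cause.** Where the 1-month value is absent because of loss of capture, system failure, revision, removal or a related death, count it as a failure in that display. Reconcile this with the exclusion for lead-related complications (13.1.2 to 13.1.6, 13.4.3; SAP 3.2 and 4.1), which otherwise removes the same subjects before they reach the display.

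The cost is a wording change in both documents and one extra row per table, with no new data collection. The displayed failure count may be less favourable.

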#### **13.4.4. Changes to Planned Analyses**

Any changes to the planned statistical analyses made prior to performing the analyses will be documented in an amended Statistical Analysis Plan. Changes from the planned statistical methods after performing the analyses will be documented in the clinical study report along with a reason for the deviation.

### **14. Data Management**

#### **14.1. Data Collection, Processing, and Review**

Subject data will be recorded in a limited access secure electronic data capture (EDC) system.

The clinical database will reside on a production server hosted by EDC System. All changes made to the clinical data will be captured in an electronic audit trail and available for review by the sponsor or its representative. The associated RAVE software and database have been designed to meet regulatory compliance for deployment as part of a validated system compliant with laws and regulations applicable to the conduct of clinical studies pertaining to the use of electronic records and signatures. Database backups are performed regularly.

The Investigator provides his/her electronic signature on the appropriate electronic case report forms (eCRFs) in compliance with local regulations. A written signature on printouts of the eCRFs must also be provided if required by local regulation. Changes to data previously submitted to the sponsor require a new electronic signature by the Investigator acknowledging and approving the changes.

Visual and/or electronic data review will be performed to identify possible data discrepancies. Manual and/or automatic queries will be created in the EDC system and will be issued to the site for appropriate response. Site staff will be responsible for resolving all queries in the database.

#### **14.2. Data Retention**

The Principal Investigator or his/her designee or Investigational site will maintain, at the investigative site, all essential study documents and source documentation that support the data collected on the study subjects in compliance with ICH/GCP guidelines and China relative regulations. Documents must be retained for 10 years after complete of the clinical study, or longer according to the individual site's requirement. BSC must retain relative clinical study documents till discontinuation of clinical use of the products.

BSC should inform the Principal Investigators and investigation sites the time period required to maintain these documents. The Principal Investigator or his/her designee will take measures to ensure that these essential documents are not accidentally damaged or destroyed. If for any reason the Principal Investigator or his/her designee withdraws responsibility for maintaining these essential documents, custody must be transferred to an individual who will assume responsibility and BSC must receive written notification of this custodial change. Sites are required to inform Boston Scientific in writing where paper or electronic files are maintained in case files are stored off site and are not readily available.

#### **15. Amendments**

If a protocol revision is necessary which affects the rights, safety or welfare of the subject or scientific integrity of the data, an amendment is required. Appropriate approvals of the

revised clinical investigational plan by Ethics Committee must be obtained prior to implementation.

## **16. Deviations**

An Investigator must not make any changes or deviate from this protocol, except to protect the life and physical well-being of a subject in an emergency. An investigator shall notify the sponsor and the reviewing EC of any major deviation from the investigational plan to protect the life or physical well-being of a subject in an emergency, and those deviations which affect the scientific integrity of the clinical investigation. Such notice shall be given as soon as possible, but no later than 5 working days after the emergency occurred, or per prevailing local requirements, if sooner than 5 working days.

All deviations from the investigational plan, with the reason for the deviation and the date of occurrence, must be documented and reported to the sponsor using EDC. Sites may also be required to report deviations to the EC, per local guidelines and government regulations.

Deviations will be reviewed and evaluated on an ongoing basis and, as necessary, appropriate corrective and preventive actions (including notification, site re-training, or site discontinuation/termination) will be put into place by the sponsor.

Deviations will be classified by BSC according to the following definitions:

- Type A - Deviation to protect the life or physical well-being of a patient in an unforeseen emergency.
- Type B - Deviation based on medical judgment.
- Type C - Deviation due to misunderstanding of protocol requirements.
- Type D - Deviation due to a situation that is beyond control.
- Type E - Deviation due to an oversight, error or protocol non-compliance.

Also, a major PD is a protocol deviation that directly or potentially disrupts the study progress (i.e., the study design, study data and results can be compromised), OR a protocol deviation that compromises the safety and welfare of study participants. A minor PD is a protocol deviation that does not disrupt study progress (i.e., the study design, study data and

results will not be compromised), AND does not compromise the safety and welfare of study participants.

## **17. Device Accountability**

The investigational devices shall be securely maintained, controlled, and used only in this clinical study. The current BSC processes will be used to track subjects and device allocations during the study.

The sponsor shall keep records to document the physical location of all investigational devices from shipment of investigational devices from BSC or designated facility/equipment to the investigation sites until return or disposal.

Records shall be kept by the investigation sites to document the physical location and conditions of storage of all investigational devices.

The principal investigator or an authorized designee shall keep records documenting the receipt, use, return and disposal of the investigational devices, which shall include the following:

- Date of receipt
- Identification of each investigational device (unique code)
- Expiry date, as applicable
- Date or dates of use
- Subject identification
- Manufacture date of investigational device
- Batch number of investigational device
- Date on which the investigational device was returned, if applicable
- Date of return of unused, expired, or malfunctioning investigational devices, if applicable.

## **18. Compliance**

### **18.1. Statement of Compliance**

This study will be conducted in accordance with ISO 14155:2011 Clinical Investigation of Medical Devices for Human Subjects-Good Clinical Practice, the relevant parts of the ICH Guidelines for Good Clinical Practice, ethical principles that have their origins in the Declaration of Helsinki, and China laws and regulations. The study shall not begin until the required approval/favorable opinion from the EC and/or regulatory authority has been obtained, if appropriate. Any additional requirements imposed by the EC or regulatory authority shall be followed, if appropriate.

### **18.2. Investigator Responsibilities**

The Principal Investigator of an investigational site is responsible for ensuring that the study is conducted in accordance with the Clinical Study Agreement, the clinical investigation plan, ISO 14155:2011, ethical principles that have their origins in the Declaration of Helsinki, any conditions of approval imposed by the reviewing EC, and prevailing local and/or country laws and/or regulations, whichever affords the greater protection to the subject.

The Principal Investigator's responsibilities include, but are not limited to, the following.

- Prior to beginning the study, sign the Clinical Study Agreement and comply with the Investigator responsibilities as described in such Agreement.
- Prior to beginning the study, sign the Investigator Brochure Signature Page (if applicable) and Protocol Signature page documenting his/her agreement to conduct the study in accordance with the protocol.
- Provide his/her qualifications and experience to assume responsibility for the proper conduct of the study and that of key members of the site team through up-to-date curriculum vitae or other relevant documentation and disclose potential conflicts of interest, including financial, that may interfere with the conduct of the clinical study or interpretation of results.

- Make no changes in or deviate from this protocol, except to protect the life and physical well-being of a subject in an emergency; document and explain any deviation from the approved protocol that occurred during the course of the clinical investigation.
- Create and maintain source documents throughout the clinical study and ensure their availability with direct access during monitoring visits or audits; ensure that all clinical-investigation-related records are retained per requirements.
- Ensure the accuracy, completeness, legibility, and timeliness of the data reported to the sponsor in the CRFs and in all required reports.
- Record, report, and assess (seriousness and relationship to the device/procedure) every adverse event as applicable per the protocol and observed device deficiency. Provide analysis report, which includes the causality assessed by both investigator and BSC and decision on study continuance, to EC per local and/or country requirements.
- Report to sponsor, per the protocol requirements, all SAEs and device deficiencies that could have led to a SADE and potential USADE or UADE.
- Report to the EC and regulatory authorities any SAEs and device deficiencies that could have led to a SADE and potential USADE or UADE, if required by the national regulations or this protocol or by the EC, and supply BSC with any additional requested information related to the safety reporting of a particular event. Provide all required source documents related to a death event to BSC and the EC per local requirements.
- Maintain the device accountability records and control of the device, ensuring that the investigational device is used only by authorized/designated users and in accordance with this protocol and instructions/directions for use.
- Allow the sponsor to perform monitoring and auditing activities, and be accessible to the clinical research monitor or auditor and respond to questions during monitoring visits or audit(s).
- Allow and support regulatory authorities and the EC when performing auditing activities.

- Ensure that informed consent is obtained in accordance with applicable laws, this protocol and local EC requirements.
- Provide adequate medical care to a subject during and after a subject's participation in a clinical study in the case of adverse events, as described in the Informed Consent Form (ICF).
- Inform the subject of the nature and possible cause of any adverse events experienced.
- As applicable, provide the subject with necessary instructions on proper use, handling, storage, and return of the investigational device when it is used/operated by the subject.
- Inform the subject of any new significant findings occurring during the clinical investigation, including the need for additional medical care that may be required.
- Provide the subject with well-defined procedures for possible emergency situations related to the clinical study, and make the necessary arrangements for emergency treatment, including decoding procedures for blinded/masked clinical investigations, as needed.
- Ensure that clinical medical records are clearly marked to indicate that the subject is enrolled in this clinical study.
- Ensure that, if appropriate, subjects enrolled in the clinical investigation are provided with some means of showing their participation in the clinical investigation, together with identification and compliance information for concomitant treatment measures (contact address and telephone numbers shall be provided).
- Inform, with the subject's approval or when required by national regulations, the subject's personal physician about the subject's participation in the clinical investigation.
- Make all reasonable efforts to ascertain the reason(s) for a subject's premature withdrawal from clinical investigation while fully respecting the subject's rights.
- Ensure that an adequate investigation site team and facilities exist and are maintained and documented during the clinical investigation.

- Ensure that maintenance and calibration of the equipment relevant for the assessment of the clinical investigation is appropriately performed and documented, where applicable.

